5.5. Monitoring Plan

A detailed plan for monitoring arrangement will be described separately from the Clinical Investigation Plan.

Monitoring will be performed by a trained person appointed by Philips to ensure compliance with the Clinical investigation plan, applicable national regulations and international standards, patient safety and data validity. The Sponsor, Philips, may designate one or more individuals to monitor the progress of a clinical study. The Sponsor may also delegate the monitoring responsibilities to a third party. However, the Sponsor remains ultimately responsible for the conduct of the study. The Institution is responsible for the appropriate de-identification of subject data. The investigational site should provide access to the source data of the subjects.

The first visit will occur as soon as possible after the first subject is enrolled at each study site. The monitoring schedule is based on the following considerations: enrollment rate, study compliance at the center, magnitude of data corrections required, complexity of the investigation, IRB/MEC request, audit/inspection.

IGT systems Best Status: Final	Clinical Investigation Plan Observational clinical study with Surgical Navigation to plan, position and check instrument placement for spine surgery interventions	XCY607-130099 2016 Sep 16 Revision: 6.0 Page 28 of 46
--	---	--

Critical data and processes will be monitored for this study prior to clinical report completion based on a risk based monitoring approach. Dependent on the risk a high or lower sample will be monitored. The monitor will review critical clinical data that affect study endpoints.

A close-out visit at a site that has enrolled subjects will be conducted once the site has completed collecting data for the study.

The monitor activities include:

- Check that the study is conducted, recorded and reported in compliance with this clinical investigation plan, and applicable regulations. Acts to oversee the progress of the study.
- Check signed and dated informed consent of the subjects and check that this is signed before any study-related procedures are undertaken.
- Ensure that essential documents (e.g. contract, MEC approval) are maintained in the Investigator Site File.
- Ensure recording of deviations from protocol and store in Investigator Site File or CRF.
- Ensure that all adverse events and device deficiencies are reported to the sponsor, and all serious adverse events and device deficiencies that could have led to a serious adverse device effect are reported to the sponsor without unjustified delay.
- Ensure that adverse event and device deficiency are reported to the MEC/IRB, if required.
- Ensure that the principal investigator is informed and knowledgeable of all relevant document updates concerning the clinical investigation (e.g. clinical investigation plan and Investigator Brochure). Ensure that amendments to the protocol and/or Investigators Brochure are provided to the MEC/IRB by the principal investigator.
- Ensure device accountability and check unapproved use outside the study.
- Source data verification is anticipated.

Names of the monitor(s) can be found in Appendix II: List of monitor(s) of this protocol. An update of this list can be provided to the site under separate cover.

5.5.1. Maintenance and calibration

The equipment relevant for the dose measurements during the clinical investigation are the Allura and DoseAwareExtend. Allura is calibrated at the time of installation and mostly after one year. DoseAwareExtend is calibrated once before providing it to the hospital. Since the duration of the study is expected to be less than one year after installation, both will not be monitored for calibration during the course of the study.

The optical cameras and the X-ray system in the Allura system will be calibrated during the installation in the hospital. Regular check will be performed by trained Philips personnel during the clinical study if recalibration of the camera and X-ray system alignment is needed.

6. STATISTICAL CONSIDERATIONS

6.1. Sample Size Justification

Mason et al (2014) reported on a meta-analysis of 30 studies evaluating screw placement using 2D, 3D, and conventional fluoroscopic image guidance systems. Using the conventional fluoroscopy, 2532 of 3719 screws were inserted accurately (68.1% accuracy); with 2D fluoroscopic navigation, 1031 of 1223 screws were inserted accurately (84.3% accuracy); and with 3D fluoroscopic navigation, 4170 of 4368 screws were inserted accurately (95.5% accuracy).

In a human cadaver study using Surgical Navigation system the accuracy was 85 % (95% CI of 72%, 95% and 74%, 96% using vertebrae within a cadaver as a cluster), compared to 64% (95% CI of 44%, 77%) for the conventional free-hand method. In another human cadaver feasibility study, 21 screws were placed using the fluoroscopy guidance system and another 21 screws using Surgical Navigation system. In 95% of insertions (20) the pedicle screws were placed in accordance with the predefined paths using the Surgical Navigation compared to 71% of the insertions with fluoro-guidance system.

IGT systems Best Status: Final	Clinical Investigation Plan Observational clinical study with Surgical Navigation to plan, position and check instrument placement for spine surgery interventions	XCY607-130099 2016 Sep 16 Revision: 6.0 Page 29 of 46
--	---	--

Assuming that the screw placement accuracy for this study will be similar to that observed in the cadaver study (i.e., 85%), a sample size of 240 screws will be required to estimate a 95% two-sided confidence interval so that the lower bound of the 95% CI is greater than the upper bound of the 95% CI observed for the cadaver study (i.e., 64% with upper bound of 95% CI of 77 with approximately 80% power (%) (i.e., approximately 5% Half Width). Assuming that the subjects will have 2 to 10 vertebrae's treated and the assumption that the majority of the patients will be scoliotic patients, approximately 15 to 25 patients will be needed to reach 240 screw placements.

Any deviation from the planned analysis described below will be documented with justification in the final clinical end report.

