2.3. Conclusion of the justification for the design of the study

There is a clear need for accurate pedicle screw placement when stabilizing the spine to prevent damage to important structures. Image-guided navigation has shown to result in significantly accurate pedicle screw placement. With Surgical Navigation we have a similar image-guided technique as described in literature, but using real-time video overlay to align an instrument with a planned path.

The positive results of pre-clinical testing and a clinical study with Surgical Navigation has provided confidence to perform a clinical study related to pedicle screw placement in humans to further evaluate Surgical Navigation. An observational pilot study using Surgical Navigation in a small group of patients undergoing a spine surgery involving pedicle screw placement is the next step in evaluating Surgical Navigation in clinical use. An observational, non-comparative study design has been chosen based on the primary objective of the study (i.e., to estimate the overall proportion of screws accurately placed with the research procedure). The outcome of the study will provide for estimation of the mean accuracy and confidence intervals for Surgical Navigation system. These result will be compared with earlier found results in the pre-clinical testing and may be used to design future studies.

Alternative studies design were evaluated but not chosen for the following reasons:

- Based on previous literature studies with procedure where pedicle screws are placed, there is a large variability between the accuracy of placing pedicle screws (mostly 68%-94%, one study even reported 28% accuracy for the standard of care method (See table 1 in the Investigator Brochure). This is due to differences in pedicle width in the different areas in the spine (cervical/higher thoracic versus lumbar) and deformation of spine (especially with scoliotic patients). So there is an expected difference for the outcome for pedicle screw placement accuracy between different subjects and between different screws within a subject.
- Randomizing treatment groups, during procedure, within a patient (i.e., left versus right side) for a paired study design that control for the between subject variability is cumbersome and may affect the

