5.3.3. Number of subjects

In total 240 screws placement are needed. It is expected that approximately 15 to 25 subjects with pedicle screw surgery are necessary to collect sufficient data for the evaluation of the primary and secondary objectives of this clinical investigation. After the first two subjects have been treated with pedicle screws there will be a delay of at least 1 week until the third and fourth subjects will be undergoing the procedure with Surgical Navigation. After subject one to four have been treated and the DMC/DSMB have been given recommendations of continuation of the study then there is no limit on how many subjects can be treated during one day. Enrollment of subjects will be stopped after approximately 240 screws are placed. This is a common number of screws used in studies showing accuracy of pedicle screw placement in the cervical²⁸. The enrollment period is expected to last for 7 months.

See section 6 Statistical considerations for more detail on the number of subjects.

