6.5. Primary objective

Objective

The primary objective of this clinical investigation is to estimate the accuracy of pedicle screw placement using Surgical Navigation based on post-procedural CBCT:

Endpoint

The primary endpoint is the accuracy of screw placement. Screw placement will be evaluated using the slightly adapted Gertzbein⁴ classification for pedicle screw breach as follows:

- grade 0 = breach 0 mm
- grade 1 = lumbar and thoracic < 2 mm, cervical <1 mm breach distance
- grade 2 = lumbar and thoracic 2-4 mm, cervical 1-2 mm breach distance
- grade 3 = lumbar and thoracic > 4 mm, cervical >2 mm breach distance

Accuracy is defined as the proportion of screws with Gertzbein grade 0 or 1. The proportion of screws accurately placed will be estimated overall, and by region (e.g., cervical, lumbar, and thoracic).

In addition, the number of lateral or medial perforations, the distance of the longitudinal axis of the screw and the planned path at the smallest diameter of the pedicle (mm), and the largest distance between screw tip and planned target of screw (mm) will be reported.

See Appendix V: Background information primary objective for more information on the primary objective.

Analysis

The primary objective for this study is to estimate the overall proportion of screws accurately placed. All subjects who underwent treatment (ITT population) will be included in the primary efficacy analysis. Analysis will be performed assuming independence among different screws within a subject using Exact Clopper-Pearson 95% confidence interval. In addition, analysis will be performed using each subject as the unit for analysis. For this analysis, a two-sided 95% CI calculated for the accuracy of screw placement will be calculated using clustered binary data methodology as described by Zhou (2011)²⁹.

In addition, the proportion of screws accurately placed will be summarized by region (e.g., cervical, lumbar, and thoracic) and by grade 0-3. The 95% confidence interval will be presented.

IGT systems Best	Clinical Investigation Plan	XCY607-130099
Status: Final	Observational clinical study with Surgical Navigation to plan, position and check instrument placement for spine surgery interventions	2016 Sep 16 Revision: 6.0 Page 30 of 46

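### The approximately 80% power stated for 240 screws does not follow from section 6.1's own inputs, which give about 88% if screws are independent

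*Protocol*

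**What the plan says.** Section 6.1 assumes that accuracy will match the 85% seen in the cadaver study. It presents 240 screws as the number required for the lower two-sided 95% limit to exceed 77%, the upper limit for the free-hand method in that study: "64% with upper bound of 95% CI of 77 with approximately 80% power (%) (i.e., approximately 5% Half Width". It names no formula, no intracluster correlation (ICC) and no design effect. It adds that "approximately 15 to 25 patients will be needed to reach 240 screw placements".

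Section 5.3.3 gives a second reason for 240, namely precedent: "This is a common number of screws used in studies showing accuracy of pedicle screw placement in the cervical".

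Section 6.5 sets out two intervals for the primary endpoint. The first is described thus: "Analysis will be performed assuming independence among different screws within a subject using Exact Clopper-Pearson 95% confidence interval". The second, introduced as an addition, takes the subject as the unit: "accuracy of screw placement will be calculated using clustered binary data methodology".

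**The concern.** Section 6.1 states every input needed to check its power figure, and section 6.5 names the interval. The check gives a power clearly above 80%, so 240 is not the number that 80% power requires on these inputs. Either an input or an allowance is missing from the text, or the percentage is off.

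What is at stake is the accuracy of a planning statement. The results may be used to design future studies (section 2.3), and a later planner who took 240 screws as the price of 80% power at 85% against 77% would be misled. A reader also cannot tell whether the power and half-width assume independent screws or allow for the subject clustering that section 6.5 recognises.

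**Working it through.** **Inputs.** From section 6.1: true accuracy p = 0.85, threshold 0.77, n = 240, two-sided 95%, 15 to 25 subjects (240/25 = 9.6 to 240/15 = 16 screws each). From section 6.5: Clopper-Pearson interval, screws independent. No ICC is given.

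**1. Half-width (reproduced).** At 204/240 = 85% the Clopper-Pearson limits are 79.84% and 89.27%, so the half-width is (89.27 − 79.84)/2 = 4.7 points. The simple normal form gives 1.96 × √(0.85 × 0.15/240) = 4.5 points. Both agree with approximately 5%.

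**2. Power (not reproduced).** The lower limit at x accurate screws is the 2.5% quantile of a Beta(x, 240 − x + 1) distribution. Power is P(X ≥ x) for X ~ Binomial(240, 0.85) at the smallest x whose lower limit exceeds 77%.

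| Accurate screws x | Lower limit | P(X ≥ x) |
|---|---|---|
| 197 | 76.64% | 91.0% |
| 198 | 77.09% | 87.9% |
| 199 | 77.55% | 84.0% |
| 200 | 78.00% | 79.4% |

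So 198 are needed, and the power is 87.9%.

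**3. Other methods, same inputs.** Wilson, Agresti-Coull and Jeffreys: 87.9%. Wald, with or without continuity correction: 91.0%. Wilson with continuity correction: 84.0%. Arcsine: 88.8%. Two-sided z-test formulas: 83.8% to 93.5%, depending on the variance used. None gives 80%.

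**4. Screws needed for 80%.** Exact power moves in a saw-tooth. It first reaches 80% at n = 195 (80.5%), falls back at 196 (79.6%) and again at 209 (79.2%), and stays at or above 80% from 210 (83.4%). The usual normal approximation gives 198.

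**5. Rounding of the inputs (Clopper-Pearson, n = 240).**

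| Threshold | Accuracy | Needed | Power |
|---|---|---|---|
| 77.49% | 85% | 199 | 84.0% |
| 77% | 84.5% | 198 | 82.8% |
| 77.2% | 84.6% | 199 | 79.4% |
| 77.49% | 84.5% | 199 | 78.1% |
| 76.5% | 85.49% | 197 | 94.1% |

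One unfavourable input leaves 83 to 84%. Both together can give about 80%.

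**6. An unstated clustering allowance.** The surplus of screws is 240/210 = 1.14 to 240/195 = 1.23. Read as a design effect 1 + (m − 1) × ICC, this corresponds to an ICC between (1.14 − 1)/(16 − 1) ≈ 0.01 and (1.23 − 1)/(9.6 − 1) ≈ 0.027. Such an allowance could explain 80%, but section 6.1 mentions none.

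**7. Subject-clustered interval (illustration; the ICCs are assumed).** Beta-binomial simulation with a ratio-estimator variance and 15 to 25 equal-sized subjects, covering both normal and t quantiles, gives power of 78 to 86% with half-width 4.8 to 5.5 points at ICC 0.02. At ICC 0.10 it gives 55 to 69% and 6.1 to 7.6 points. A plain design-effect formula shows the same pattern with lower power (77 to 82%, then 45 to 59%).

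**The case against.** - **Unreproduced is not the same as wrong.** The cadaver results appear only as whole percents, and their unrounded values may lie in redacted text. Rounding of both inputs spans 78 to 94%, which contains 80%. This stands. A reader might infer that the sponsor made an arithmetic mistake; the document does not show that.

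- **A whole-percent criterion.** If the lower limit had to reach 78%, then 200/240 would be needed and the power would be 79.4%. This fails as a reading of rounded figures: at 199/240 the limit is 77.55%, which already rounds to 78%, and the power is then 84.0%.

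- **A different planning formula.** A z-test with null variance only, or with continuity correction, comes to about 79 to 81% when just one input sits at its rounding limit (77.5% or 84.5%). That is possible, but section 6.1 names no such formula and section 6.5 plans an exact interval. It is a further reason to ask for the basis of the figure.

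- **Little depends on it.** Section 6.5 tests nothing against 77%, section 4.2 closes by ruling out pass or fail criteria, the half-width is right, and section 5.3.3 supports 240 independently. This stands and limits the weight of the point.

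- **Clustering is handled in the analysis.** Section 6.5 adds the subject-clustered interval, section 6.1 does not claim that its power applies to it, and expected precision over assumed ICCs can be left to a SAP. This largely stands. A reader might infer from "there is an expected difference for the outcome for pedicle screw placement accuracy between different subjects and between different screws within a subject" in section 2.3 that the study is underpowered. The document gives no ICC to support that. Its only clustered interval shows no widening ("95% CI of 72%, 95% and 74%, 96% using vertebrae within a cadaver as a cluster"), although the cluster there is the vertebra, so it does not settle the matter for subjects either.

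**Conclusion.** The point holds as a minor one. On the inputs as written, with Clopper-Pearson and independent screws, power is about 88% against the stated 80%, and 80% needs about 195 to 210 screws where 240 are called required. The stated half-width is consistent with 4.7 points. With this interval, 80% follows only from unfavourable rounding of both inputs or from a clustering allowance that is not stated.

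For the independence interval the stated power is conservative, so the point gives no ground for doubting that 240 screws suffice there. The exact results depend only on figures in the protocol. The clustered range depends on assumed ICCs and on the method chosen, and carries no weight beyond illustration.

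**What to change.** Change section 6.1 only, in one of two ways:

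1. Restate the power as about 88% with a half-width of about 4.7 points, and say that both assume independent screws; or
2. Keep 80% and state the unrounded accuracy and threshold, or the design effect, that produce it.

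If the unrounded cadaver values do lead to 80%, the second is the right choice.

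Optionally, add a sentence that both figures are less favourable for the subject-clustered interval of section 6.5, with the ICC range labelled as assumed. For ICC 0.02 to 0.10 and 15 to 25 subjects, power runs from about 86% down to 55% and half-width from about 4.8 to 7.6 points.

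The cost is a few lines of wording, with no extra patients and no change to the analysis. The optional sentence will make the planned precision look less favourable.

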6.2. General Consideration

The primary analysis of safety and efficacy will be performed including all subjects who underwent treatment (ITT population). All variables will be summarized by descriptive statistics. The statistics for continuous variables includes mean, median, standard deviation, 95% confidence interval for the means, and the number of observations. For categorical variables, number events, event rate, and 95% confidence interval for the event rate will be presented.

6.3. Subject disposition

Subject disposition, including the total number of subjects evaluated will be presented. In addition, a listing will be provided with the reasons for why the subject was not evaluated.

6.4. Demographics and Baseline Characteristics

Basic subject characteristics such as age, gender, height and weight will be summarized. In addition, the main reason for surgery will be presented.

6.5. Primary objective

Objective

The primary objective of this clinical investigation is to estimate the accuracy of pedicle screw placement using Surgical Navigation based on post-procedural CBCT:

Endpoint

The primary endpoint is the accuracy of screw placement. Screw placement will be evaluated using the slightly adapted Gertzbein⁴ classification for pedicle screw breach as follows:

- grade 0 = breach 0 mm
- grade 1 = lumbar and thoracic < 2 mm, cervical <1 mm breach distance
- grade 2 = lumbar and thoracic 2-4 mm, cervical 1-2 mm breach distance
- grade 3 = lumbar and thoracic > 4 mm, cervical >2 mm breach distance

Accuracy is defined as the proportion of screws with Gertzbein grade 0 or 1. The proportion of screws accurately placed will be estimated overall, and by region (e.g., cervical, lumbar, and thoracic).

In addition, the number of lateral or medial perforations, the distance of the longitudinal axis of the screw and the planned path at the smallest diameter of the pedicle (mm), and the largest distance between screw tip and planned target of screw (mm) will be reported.

See Appendix V: Background information primary objective for more information on the primary objective.

Analysis

The primary objective for this study is to estimate the overall proportion of screws accurately placed. All subjects who underwent treatment (ITT population) will be included in the primary efficacy analysis. Analysis will be performed assuming independence among different screws within a subject using Exact Clopper-Pearson 95% confidence interval. In addition, analysis will be performed using each subject as the unit for analysis. For this analysis, a two-sided 95% CI calculated for the accuracy of screw placement will be calculated using clustered binary data methodology as described by Zhou (2011)²⁹.

In addition, the proportion of screws accurately placed will be summarized by region (e.g., cervical, lumbar, and thoracic) and by grade 0-3. The 95% confidence interval will be presented.

IGT systems Best	Clinical Investigation Plan	XCY607-130099
Status: Final	Observational clinical study with Surgical Navigation to plan, position and check instrument placement for spine surgery interventions	2016 Sep 16 Revision: 6.0 Page 30 of 46

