 - d. During preparation and acquisition of CBCT for confirmation
 - e. Average procedure dose per planned path
- 6) To estimate the total radiation dose (effective dose) received by operator, if DoseAware Xtend is available.
- 7) To describe procedure related complications
- 8) Report all adverse events
- 9) Report all adverse device effects
- 10) Report all device deficiencies that could have led to a serious adverse event

Primary and secondary endpoints

The primary endpoint of the study is accuracy.

- 1) This is measured according to an adapted version of the in literature reported classification method by Gerztbein, so that it includes distance of breaches applicable for cervical region besides the lumbar and thoracic region.

Furthermore, accuracy will also be reported by direction of breach (lateral/medial), and distance between planned path and screw in smallest area of the pedicle (mm) and the distance between screw tip and planned target of screw (mm).

Secondary endpoints are:
Procedure time, time to insert a pedicle screw, Length of hospital Stay, System Usability Score, patient radiation dose (DAP and AK and fluoro time), occupational radiation dose (effective dose), procedure related complications, adverse events, adverse device effects, device deficiencies that could have led to a serious adverse event.

Main inclusion criteria

- Subject will be undergoing a spine surgery with pedicle screw placement
- Subject is 16 years of age or older
- Subject is able to give informed consent

Main exclusion criteria

- Subject participates in a potentially confounding device or drug trial during the course of the study.
- Subject meets an exclusion criteria according to national law (e.g. pregnant woman, breast feeding woman)

No. of subjects

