Status: Final	Observational clinical study with Surgical Navigation to plan, position and check instrument placement for spine surgery interventions	

All post-procedural CBCT acquisitions will be evaluated by an independent reviewer (neurosurgeon, orthopedic surgeon or spine surgeon experienced in pedicle screw placements) to determine the accuracy of pedicle screw placement according to the modified Gertzbein grading system (grade 0-3, see section 4.1) and direction (lateral/medial breach).

Furthermore, the distance (mm) between the following two points will be measured:

- The planned path and screw axis at smallest pedicle diameter
- The planned path and at the tip of the screw

The classification by the independent reviewer will be used for the objectives.

[figure not shown]

Figure 8: Flowchart for patient undergoing pedicle screw placement

Workflow feedback and usability information

Observations related to the workflow for the spine procedure will be performed by a Philips representative during some of the procedures. Workflow feedback will also be obtained through a short interview with the physician performing the procedure.

At the end of the study the physician(s) performing the procedure will be requested to complete a System Usability Scale (SUS) questionnaire to obtain general information related to the usability of Surgical Navigation related to these spine procedures.

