APPENDIX V: BACKGROUND INFORMATION PRIMARY OBJECTIVE

The classification system used in this study is as follows:

- grade 0 = breach 0 mm
- grade 1 = lumbar and thoracic < 2 mm, cervical <1 mm breach distance
- grade 2 = lumbar and thoracic 2-4 mm, cervical 1-2 mm breach distance
- grade 3 = lumbar and thoracic > 4 mm, cervical >2 mm breach distance

This classification system describes the distance of breach. This is measured according to an adapted version of the in literature reported classification method by Gerztbein. This classification system is used for lumbar and thoracic region and is for this study adapted to also include the distance of the breach for pedicles placed in the cervical area.

Furthermore the direction of perforation is interesting to measure (lateral or medial breach), since the consequences of the breach in a different direction might lead to different complications. Therefore additional information will be collected to report on the direction of perforation.

Additionally, the distance between the planned path and the longitudinal axis of the screw indicate how accurate the pedicle screw can be placed according to the planned path. When using the distance between planned path and longitudinal axis of the screw in smallest area of the pedicle (mm), one measures at the most critical point in the pedicle. When measuring the distance between screw tip of the screw and the planned target of screw (mm), this is measured at the somewhat less critical point at the point of the screw.

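### Does the inconsistent wording of the supplementary screw-tip distance need a change to the plan?

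*Protocol*

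**What the plan says.** The protocol mentions a distance at the screw tip in six places, with three wordings.

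- **Measurement instruction** (section 5.4, repeated in the Summary under study procedures). After the paragraph on the independent reviewer, two distances in mm are listed. The first is "The planned path and screw axis at smallest pedicle diameter"; the second is "The planned path and at the tip of the screw".
- **Reporting statement** (sections 5.1 and 6.5): "the largest distance between screw tip and planned target of screw (mm) will be reported".
- **Endpoint list and background** (Summary, primary and secondary endpoints; Appendix V). The Summary has "the distance between screw tip and planned target of screw (mm" and Appendix V has "When measuring the distance between screw tip of the screw and the planned target of screw (mm", both without *largest*. Section 6.5 refers to Appendix V for more on the primary objective.

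The primary endpoint is separate: "Accuracy is defined as the proportion of screws with Gertzbein grade 0 or 1". The breach direction and the two distances come after it as extra items, introduced by "In addition, the number of lateral or medial perforations". For continuous variables in general, section 6.2 states: "The statistics for continuous variables includes mean, median, standard deviation, 95% confidence interval for the means", together with the number of observations.

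**The concern.** Two features look like real contradictions.

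1. **End points of the measurement.** A distance from the planned path to the tip is measured to a line and ignores how deep the screw went. A distance from the tip to the planned target is measured between two points and includes depth. If the reviewer follows section 5.4 literally while the report follows section 6.5, what is recorded is not what is reported. Alternatively, depth differences enter a figure that readers take as alignment error.
2. **The word *largest*.** Sections 5.1 and 6.5 do not say what it is taken over: image planes for one screw, the screws of one subject, or all screws. A maximum grows with the number of screws. A single overall maximum has no mean, standard deviation or confidence interval of the kind section 6.2 plans.

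At stake is the meaning of one published distance. Section 2.3 says the study's results will be compared with pre-clinical results and may inform later studies, so an ambiguous figure could be carried forward.

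**Working it through.** The protocol gives no numerical value for this measure, so there is no figure to reproduce. The check asks whether the wordings can differ in number, whether the text shows which is meant, and what depends on the answer.

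**1. Can the wordings differ?** Let *e* be the off-axis distance of the tip from the planned path and *d* the depth difference along the path. Then

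- path to tip = *e*
- tip to target = √(*e*² + *d*²)

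With *e* = 2 mm (assumed; the protocol gives no tip or depth errors):

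| *d* (mm) | path to tip (mm) | tip to target (mm) |
|---|---|---|
| 0 | 2.00 | √4 = 2.00 |
| 1 | 2.00 | √5 = 2.24 |
| 2 | 2.00 | √8 = 2.83 |
| 3 | 2.00 | √13 = 3.61 |

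They agree only when *d* = 0, so the literal readings are different quantities.

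**2. How much could *largest* matter?** Section 6.1 expects 240 screws in about 15 to 25 subjects, which is 240/25 = 9.6 to 240/15 = 16 screws per subject. Assume three independent normal error components with equal SD. The expected maximum divided by the mean is then 1.70 for 10 screws, 1.82 for 16 and 2.37 for 240. If *largest* means the largest reading for one screw, none of these ratios applies.

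**3. Does *largest* conflict with section 6.2?** Take the three scopes in turn.

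- Largest reading per screw: about 240 values, for which mean, median, SD and confidence interval are all available.
- Largest per subject: about 15 to 25 values, again summarisable as section 6.2 states.
- Largest over all screws: one value, which cannot be summarised that way.

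Only the third conflicts. It is also the least natural reading, since the plan otherwise describes continuous variables by mean, median and SD.

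**4. Which end points are meant?**

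| Place | Role | End points | *Largest*? |
|---|---|---|---|
| Summary, endpoints | endpoint list | tip, planned target | no |
| Section 5.1 | reporting | tip, planned target | yes |
| Section 6.5 | reporting | tip, planned target | yes |
| Appendix V | background cited by 6.5 | tip, planned target | no |
| Section 5.4 and its Summary copy | procedure | planned path, tip | no |

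Every place that defines or reports the quantity names the tip and the planned target. The exception is one bullet, printed twice, and it is ungrammatical. Its lead-in speaks of a distance between two points, which suits tip and target better than tip and line. That is not decisive, because the first bullet under the same lead-in is path to axis. Still, the simplest reading of the second bullet is the end of the planned path against the tip of the screw.

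**5. What depends on it?** The primary proportion uses breach grades only. The Clopper-Pearson interval, the clustered interval and the 240-screw justification are built on that proportion. The companion distance at the narrowest part of the pedicle has consistent end points throughout. None of these uses the tip distance.

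**The case for a change.** The best case for a change is that this is a conflict within the protocol, not a detail left to an analysis plan. If the reviewer recorded only the perpendicular distance, no later document could recover the depth component without reading the images again, for up to 240 screws. Section 6.5 also disagrees with the appendix it cites over *largest*, and reading the section 5.4 bullet charitably does not explain that word. Correcting the text would cost very little.

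The inconsistency itself stands: the quotations are exact and all come from current text. It is also true that a literal reading of section 5.4 would lose depth. The practical risk is small, though. A reviewer would have to follow one garbled bullet against the endpoint list, the reporting statements and the appendix. The millimetre illustrations do not raise the stakes either, because the offsets, depth differences and error distribution are all assumed.

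Two further remedies do not follow from a wording slip. Recording depth in a separate field is a preference about what to collect. A cluster-adjusted interval for the mean tip distance is a detail commonly left to a statistical analysis plan, which is not at hand here.

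**Conclusion.** This is a clerical inconsistency in a supplementary descriptive measure, and no change to the plan follows. A sensible analyst would take the per-screw distance from tip to planned target, as the endpoint list and Appendix V have it, and summarise it as section 6.2 prescribes. If *largest* was meant as the largest reading per screw or per subject, the same summaries still work, provided the report says which was used.

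The effect on the primary result is nil: the grade 0 or 1 proportion, both of its confidence intervals and the 240-screw size are unchanged. The effect on the tip distance could reach the sizes shown above, but only under the literal reading of section 5.4 or a maximum taken over screws, and only with the assumed errors. Appendix V itself treats the tip as less critical than the narrowest part of the pedicle, and no hypothesis, threshold or pass criterion rests on the tip distance.

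The conclusion assumes that the section 5.4 bullet means the end point of the planned path. The text supports this but does not say so outright.
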